6.1.1.2. Active Treatment Period – Month 3 to Month 96 Visits

For subjects in the active treatment period, study visits will be scheduled at the study site at Months 3, 6, 9, 12, 15, 18, 21, 24, 27, 30, 33, 36, 39, 42, 45, 48, 51, 54, 57, 60, 63, 66, 69, 72, 75, 78, 81, 84, 87, 90, 93, and 96 (within ± 14 days of the projected visit date based on the actual baseline visit date).

The following safety and efficacy evaluations will be performed at all visits during the active treatment period unless otherwise indicated:

1. Collect/update contact information, including primary care physician or other treating physician.
2. Concomitant medications (DMARDs, corticosteroids, NSAIDs, and anti-infective agents) and non-drug treatments received due to an adverse event.
3. Physical examination (performed by a physician at months 12, 24, 36, 48, 60, 72, 84, and 96 only).
 - The physical examination will include completion of the Tanner Assessment for subjects < 18 years or who have a score of < 5 on 1 or more applicable domain(s).
4. Vital signs: Temperature, blood pressure (mmHg) and pulse rate (beats/min, after sitting for at least 5 minutes).
5. Height (cm, at months 12, 24, 36, 48, 60, 72, 84, and 96 only).
6. Weight (kg):
 - For subjects who are < 18 years of age and who weigh ≤ 62 kg (at all visits).
 - For subjects who are ≥ 18 years of age or weigh > 62 kg (at months 12, 24, 36, 48, 60, 72, 84, and 96 only).
7. Laboratory evaluations (ie, hematology, blood chemistry, and CRP, at months 6, 12, 18, 24, 30, 36, 42, 48, 54, 60, 66, 72, 78, 84, 90, and 96 only). Additional testing may be performed according to local guidelines or standard of care and for follow-up of abnormal laboratory test results.
8. For female subjects, evaluate childbearing potential. The evaluation must be documented in the subject's source documents.
9. Female subjects who, in the opinion of the investigator, are of childbearing potential will have a urine pregnancy test at each visit; this includes subjects who are

- menstruating at the time of the visit. For these subjects, a negative test result must be available before dispensing and/or administration of investigational product. Pregnancy tests will also be done whenever one menstrual cycle is missed during the active treatment period or when potential pregnancy is otherwise suspected. Pregnancy tests may also be repeated as per request of IRB/IECs or if required by local regulations.
10. As appropriate, discuss sexual activity. For those subjects who either plan on becoming sexually active or who are sexually active, discuss highly effective methods of contraception (refer to [Section 4.3.2](#) for female subjects and [Section 4.3.3](#) for male subjects). The discussion must be documented in the subject's source documents.
 11. PGA of Disease Activity (at months 6, 12, 18, 24, 30, 36, 42, 48, 54, 60, 66, 72, 78, 84, 90, and 96 only).
 12. Patient/Parent Global Assessment, according to the subject's age at the time of the assessment (at months 6, 12, 18, 24, 30, 36, 42, 48, 54, 60, 66, 72, 78, 84, 90, and 96 only).
 13. Pain Assessment. The Pain Assessment should be completed before the Joint Assessment (at months 6, 12, 18, 24, 30, 36, 42, 48, 54, 60, 66, 72, 78, 84, 90, and 96 only).
 14. Duration of Morning Stiffness (at months 6, 12, 18, 24, 30, 36, 42, 48, 54, 60, 66, 72, 78, 84, 90, and 96 only).
 15. Joint Assessment (at months 6, 12, 18, 24, 30, 36, 42, 48, 54, 60, 66, 72, 78, 84, 90, and 96 only).
 16. Overall Back Pain and Nocturnal Back Pain (at months 6, 12, 18, 24, 30, 36, 42, 48, 54, 60, 66, 72, 78, 84, 90, and 96 only [ERA subjects only]).
 17. BASMI Assessments (at months 6, 12, 18, 24, 30, 36, 42, 48, 54, 60, 66, 72, 78, 84, 90, and 96 only [ERA subjects only]).
 18. BSA (at months 6, 12, 18, 24, 30, 36, 42, 48, 54, 60, 66, 72, 78, 84, 90, and 96 only [PsA subjects only]).
 19. PGA of Psoriasis (at months 6, 12, 18, 24, 30, 36, 42, 48, 54, 60, 66, 72, 78, 84, 90, and 96 only [PsA subjects only]).
 20. CHAQ or HAQ, according to the subject's age at the time of the assessment (at months 6, 12, 18, 24, 30, 36, 42, 48, 54, 60, 66, 72, 78, 84, 90, and 96 only).
 21. Adverse events, including malignancies, serious adverse events, infections, medically important infections, and injection site reactions.

22. Perform drug accountability.
23. Collect and review diary card dispensed at the previous visit.
 - For each dose, the site personnel will calculate the total volume (mL) delivered from the syringe(s) and the total dose (mg).
24. Use the IWR/IVR to allocate investigational product packages (except at month 96).
25. Dispense investigational product, investigational product instructions, and the subject diary (except at month 96).
26. Dispense the reminder card for next scheduled visit.
27. Complete the End of Treatment Subject Summary CRF (only at month 96).

6.1.2. Withdrawal/Re-treatment Period

6.1.2.1. Baseline Procedures for Subjects Planning to Enter Directly into the Withdrawal/Re-treatment Period

The following section is only applicable to subjects who enter directly into the withdrawal/re-treatment period at the baseline visit of study B1801023.

Baseline procedures may not commence until after the informed consent and assent (as applicable) have been signed. The study investigator or a sub-investigator will discuss with each subject and parent(s) (as applicable according to subject age and local guidelines) the nature of the study, its requirements, and its restrictions.

Every attempt should be made to complete the study B1801023 baseline visit on the same day as the study 0881A1-3338 week 96 visit. The baseline visit (day 1) must occur within 14 days of the last dose of investigational product received in study 0881A1-3338.

The following baseline procedures and assessments must be completed for all subjects entering into the withdrawal/re- treatment period:

1. Sign and date informed consent/assent for withdrawal/re-treatment period.
2. Review inclusion/exclusion criteria that apply to all subjects and that apply to subjects planning to enter the withdrawal/re-treatment period.
 - Those subjects who do not meet entry criteria for withdrawal/re-treatment period may be evaluated to determine whether participation in the active treatment period or observational period is appropriate.
3. Collect/update contact information, including primary care physician or other treating physician every.

4. For female subjects, evaluate childbearing potential. The evaluation must be documented in the subject's source documents.
5. Female subjects who, in the opinion of the investigator, are of childbearing potential will have a urine pregnancy test, which must be performed within 7 days before the baseline visit; this includes subjects who are menstruating at the time of the visit. If a pregnancy test was collected at the week 96 visit in study 0881-3338, and the visit occurred within 7 days of the baseline visit, a urine pregnancy test does not have to be repeated as long as the test result was negative. For these subjects, a negative test result must be available before dispensing and administration of investigational product. Pregnancy tests will also be done whenever one menstrual cycle is missed during the active treatment period or when potential pregnancy is otherwise suspected. Pregnancy tests may also be repeated as per request of IRB/IECs or if required by local regulations.
6. As appropriate, discuss sexual activity. For those subjects who either plan on becoming sexually active or who are sexually active, discuss requirement for highly effective methods of contraception (refer to [Section 4.3.2](#) for female subjects and [Section 4.3.3](#) for male subjects). The discussion must be documented in the subject's source documents.
7. BASMI and its components (Intermalleolar Distance, Cervical Rotation, Modified Schober's Test, Lateral Flexion, and Tragus to Wall Distance) only for ERA subjects.
8. Prior and concomitant medications (DMARDs, corticosteroids, NSAIDs, and anti-infective agents) and non-drug treatments received due to an adverse event. Medications reported as ongoing at the final study 0881A1-3338 visit as well as events starting between the final study 0881A1-3338 visit and baseline visit of study B1801023 must be recorded on the appropriate CRF.
9. Adverse events, including malignancies, serious adverse events, infections, medically important infections, and injection site reactions. Events reported as ongoing at the final study 0881A1-3338 visit as well as events starting between the final study 0881A1-3338 visit and baseline visit of study B1801023 must be recorded on the appropriate CRF.
10. Registration/Randomization.
11. Dispense reminder card for next scheduled visit.

The following additional baseline procedures and assessments do not need to be completed for subjects in the withdrawal/re-treatment period as long as the each procedure was completed within 14 days of the study 0881A1-3338 week 96 visit and the study B1801023 baseline visit:

12. Physical examination (performed by a physician).

- The physical examination will include completion of the Tanner Assessment for subjects <18 years or who have a score of <5 on 1 or more applicable domain(s).
13. Vital signs: Temperature, blood pressure (mmHg) and pulse rate (beats/min, after sitting for at least 5 minutes).
 14. Height.
 15. Weight (kg).
 16. Laboratory evaluations (ie, hematology, blood chemistry, and CRP).
 17. PGA of Disease Activity.
 18. Patient/Parent Global Assessment, according to the subject's age at the time of the assessment.
 19. Pain Assessment. The Pain Assessment should be completed before the Joint Assessment.
 20. Duration of Morning Stiffness.
 21. Joint Assessment including joints with limitation of motion.
 22. Overall Back Pain and Nocturnal Back Pain (ERA subjects only).
 23. BSA (PsA subjects only).
 24. PGA of Psoriasis (PsA subjects only).
 25. CHAQ or HAQ, according to the subject's age at the time of the assessment.

6.1.2.2. Withdrawal Period

Subjects who are eligible and consent to participate in the withdrawal period will have the following visits conducted:

- Subjects who enter directly into the withdrawal period will have the first post baseline visit conducted at the study site 1 month (± 7 days) after the baseline visit.
- Subjects who participated in the active treatment period of study B1801023 will have the first withdrawal visit conducted at the study site 1 month (± 7 days) after the active treatment early withdrawal visit.
- Subsequent visits will occur at the study site every 3 months after the baseline or active treatment early withdrawal visit for up to a year and then every 6 months thereafter. Subsequent visits must be scheduled within ± 14 days of the projected visit date based on the actual date of the baseline or active treatment period early

withdrawal visit. Subjects who do not experience disease relapse will continue in the withdrawal period for a total of 96 months from the time of the baseline visit in study B1801023.

The following assessments will be performed at all visits during the withdrawal period unless otherwise indicated:

1. Ensure that the subject meets inclusion/exclusion criteria that apply to the withdrawal period.
2. Those subjects who do not meet entry criteria for the withdrawal period will be asked to participate in the observational period.
3. Ensure the most recent version(s) of the informed consent/assent for withdrawal/re-treatment period has been signed and dated.
4. Collect/update contact information, including primary care physician or other treating physician.
5. Concomitant medications (DMARDs, corticosteroids, NSAIDs, and anti-infective agents) and non-drug treatments received due to an adverse event.
6. Physical examination (performed by a physician and conducted at months 12, 24, 36, 48, 60, 72, 84, and 96 only).
 - The physical examination will include completion of the Tanner Assessment for subjects <18 years or who have a score of <5 on 1 or more applicable domain(s).
7. Vital signs: Temperature, blood pressure (mmHg) and pulse rate (beats/min, after sitting for at least 5 minutes).
8. Height (cm, at months 12, 24, 36, 48, 60, 72, 84, and 96 only).
9. Weight (kg):
 - For subjects who are <18 years of age and who weigh ≤ 62 kg (at all visits).
 - For subjects who are ≥ 18 years of age or weigh > 62 kg (at months 12, 24, 36, 48, 60, 72, 84, and 96 only).
10. Laboratory evaluations (ie, hematology, blood chemistry, and CRP).
11. For female subjects, evaluate childbearing potential. The evaluation must be documented in the subject's source documents.
12. Female subjects who, in the opinion of the investigator, are of childbearing potential will have a urine pregnancy test; this includes subjects who are menstruating at the time of the visit. Pregnancy tests will also be done whenever one menstrual cycle is

- missed during the withdrawal period or when potential pregnancy is otherwise suspected. Pregnancy tests may also be repeated as per request of IRB/IECs or if required by local regulations.
13. As appropriate, discuss sexual activity. For those subjects who either plan on becoming sexually active or who are sexually active, discuss highly effective methods of contraception (refer to [Section 4.3.2](#) for female subjects and [Section 4.3.3](#) for male subjects). The discussion must be documented in the subject's source documents.
 14. PGA of Disease Activity.
 15. Patient/Parent Global Assessment, according to the subject's age at the time of the assessment.
 16. Pain Assessment. The Pain Assessment should be completed before the Joint Assessment.
 17. Duration of Morning Stiffness.
 18. Joint Assessment.
 19. Overall Back Pain and Nocturnal Back Pain (ERA subjects only).
 20. BASMI Assessments (ERA subjects only).
 21. BSA (PsA subjects only).
 22. PGA of Psoriasis (PsA subjects only).
 23. CHAQ or HAQ, according to the subject's age at the time of the assessment.
 24. Adverse events, including malignancies, serious adverse events, infections, medically important infections, and injection site reactions.
 25. Dispense reminder card for next scheduled visit (except at month 96).
 26. Complete the End of Phase Subject Summary CRF for the withdrawal period (at the month 96 visit only).
 27. Complete the End of Study Summary CRF (at the month 96 visit only).

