- b. Subjects who remain eligible for re-treatment will continue in the re-treatment period for a total of 96 months (± 14 days) from the time of the baseline visit in study B1801023.
- c. Subjects in the re-treatment period who withdraw from investigational product for any reason before completion of the Month 96 visit are required to complete the retreatment early withdrawal visit at the study site. At that time, the subject will be asked to participate in the observational period. Subjects may not enter the withdrawal/re-treatment period more than once during the study.
- d. The follow-up visit will only completed for subjects who are receiving investigational product in either the active treatment period or the re-treatment period approximately 96 months after the baseline visit in study B1801023 and will occur at the study site 30 days (± 7 days) after the Month 96 visit.
- e. Subjects who receive at least 1 dose of investigational product in the re-treatment period of study B1801023 and withdraw from the re-treatment period before completion of the month 96 visit will be asked to be followed in the observational period for a total of 96 months from the time of the baseline visit in study B1801023. Once the subject is in the observational period, he or she cannot resume investigational product for the remaining time in the study.
- f. For subjects who agree to participate in the observational period, the first observational visit will occur at the study site and will be scheduled 30 days (± 7 days) after the retreatment early withdrawal visit.
- g. Subsequent observational visits will occur by telephone every 6 months (± 4 weeks) after the first observational visit. For subjects < 18 years of age, telephone contacts will be conducted with the subject's parent or legal representative/guardian. For subjects aged ≥ 18 years, telephone contacts will be conducted with the subject or the subject's parent or legal representative/guardian. The number of telephone contacts will be adjusted based on when the subject enters the observational period.
- h. The final observational visit will occur by telephone contact 96 months (± 4 weeks) after the baseline visit of study B1801023.
- i. Applies to the Month 3 visit.

- j. For subjects in the re-treatment period, the following concomitant medications will be collected: DMARDs, corticosteroids, NSAIDs, and anti-infective agents. Only non-drug treatments received due to an adverse event will be collected.

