6. Other severe acute or chronic medical or psychiatric condition or laboratory abnormality that may increase the risk associated with study participation or investigational product administration or may interfere with the interpretation of study results and, in the judgment of the investigator, would make the subject inappropriate for entry into this study.
7. Signs and symptoms or suspicion of active tuberculosis.

4.2.3. Additional Exclusion Criteria for Subjects Planning to Enter in the Withdrawal/Re-treatment Period

1. Withdrawal from investigational product in study 0881A1-3338 for any reason.
2. Prior and/or current participation in the observational period of study B1801023.
3. Prior and/or current participation in the withdrawal/re-treatment period of study B1801023.

4.2.3.1. Additional Exclusion Criteria for Subjects Planning to Restart Investigational Product in the Re-treatment Period

1. History of malignancy other than squamous cell, basal cell carcinoma or cervical carcinoma in situ.

2. Participation in other clinical studies of investigational drugs or investigational combinations of approved drugs during participation in study B1801023.
3. Pregnant or breastfeeding female subjects.
4. Receipt of any of the following during participation in study B1801023:
 - Any immunosuppressive biologic drugs, including but not limited to TNF inhibitors (other than etanercept), abatacept, rituximab, anakinra and tocilizumab;
 - Immunosuppressive drugs (excluding corticosteroids) (eg, cyclophosphamide, cyclosporine, azathioprine);
 - Leflunomide;
 - Use of more than 1 of the non-biologic DMARDs permitted in study B1801023 (ie, methotrexate, hydroxychloroquine, chloroquine, sulfasalazine) in subjects <18 years of age;
 - Use of more than 2 of the non-biologic DMARDs permitted in study B1801023 (ie, methotrexate, hydroxychloroquine, chloroquine, sulfasalazine) or hydroxychloroquine and chloroquine taken at the same time in subjects ≥ 18 years of age;
 - Non-biologic DMARDs other than those permitted in study B1801023 (ie, methotrexate, hydroxychloroquine, chloroquine, sulfasalazine), or those not listed under other exclusion criteria;
5. Receipt of any live (attenuated) vaccine within 4 weeks after the last dose of investigational product in active treatment period and within 8 weeks prior to the first dose of investigational product in the re-treatment period.
6. Any of the following laboratory abnormalities based on the most recent laboratory results:

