 - White blood cell (WBC) count $< 3.50 \times 10^3/\text{mm}^3$ (SI units: $< 3.50 \times 10^9/\text{L}$) and neutrophils $< 1 \times 10^9/\text{L}$;
 - Hemoglobin $< 8.5 \text{ g/dL}$ (SI units: $< 85 \text{ g/L}$);
 - Platelet Count $< 125,000/\text{mm}^3$ or $\geq 1,000,000/\text{mm}^3$ (SI units: $< 125 \times 10^9/\text{L}$ or $\geq 1,000 \times 10^9/\text{L}$);
 - Aspartate aminotransaminase (AST) or alanine aminotransaminase (ALT) $\geq 2.0 \times$ upper limit of normal (ULN);

- Should the laboratory results drawn at the time of re-treatment shows that the subject has met any of the above laboratory exclusions, the subject may be withdrawn from investigational product at that time (refer to [Section 6.1.4](#)).
7. Other severe acute or chronic medical or psychiatric condition or laboratory abnormality that may increase the risk associated with study participation or investigational product administration or may interfere with the interpretation of study results and, in the judgment of the investigator, would make the subject inappropriate for entry into the re-treatment period of this study.
 8. Signs and symptoms or suspicion of active tuberculosis.

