6.1.2.3. Re-Treatment Period

Subjects who are eligible for re-treatment with investigational product will have study visits conducted at the study site every 3 months after the re-treatment assessment visit. Visits must be scheduled within ± 14 days of the projected visit date based on the actual date of the re-treatment assessment visit. Subjects who remain eligible for re-treatment will continue in

the re-treatment period for a total of 96 months (± 14 days) from the time of the baseline visit in study B1801023.

The following assessments will be performed at all visits during the re-treatment period:

1. Ensure that the subject meets the inclusion/exclusion criteria that apply to the re-treatment period.
2. Those subjects who do not meet entry criteria for the re-treatment period will be asked to participate in the observational period.
3. Ensure the most recent version(s) of the informed consent/assent for withdrawal/re-treatment period has been signed and dated.
4. Collect/update contact information, including primary care physician or other treating physician.
5. Concomitant medications (DMARDs, corticosteroids, NSAIDs, and anti-infective agents) and non-drug treatments received due to an adverse event.
6. Physical examination (performed by a physician and conducted at months 12, 24, 36, 48, 60, 72, 84, and 96 months only).
 - The physical examination will include completion of the Tanner Assessment for subjects <18 years or who have a score of <5 on 1 or more applicable domain(s).
7. Vital signs: Temperature, blood pressure (mmHg) and pulse rate (beats/min, after sitting for at least 5 minutes).
8. Height (cm, at months 12, 24, 36, 48, 60, 72, 84, and 96 only).
9. Weight (kg):
 - For subjects who are <18 years of age and who weigh ≤ 62 kg (at all visits).
 - For subjects who are ≥ 18 years of age or weigh > 62 kg (at months 12, 24, 36, 48, 60, 72, 84, and 96 only).
10. Laboratory evaluations (ie, hematology, blood chemistry, and CRP) at months 3, 6, 9, 12, and every 6 months thereafter.
11. For female subjects, evaluate childbearing potential. The evaluation must be documented in the subject's source documents.
12. Female subjects who, in the opinion of the investigator, are of childbearing potential will have a urine pregnancy test; this includes subjects who are menstruating at the time of the visit. Pregnancy tests will also be done whenever one menstrual cycle is

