tests should be repeated and decisions regarding continuation of investigational product must be discussed with the sponsor's Clinical team.

8. For female subjects, evaluate childbearing potential. The evaluation must be documented in the subject's source documents.
9. Female subjects who, in the opinion of the investigator, are of childbearing potential will have a urine pregnancy test; this includes subjects who are menstruating at the time of the visit. Pregnancy tests will also be done whenever one menstrual cycle is missed during the active treatment period or when potential pregnancy is otherwise suspected. Pregnancy tests may also be repeated as per request of IRB/IECs or if required by local regulations.
10. As appropriate, discuss sexual activity. For those subjects who either plan on becoming sexually active or who are sexually active, discuss highly effective methods of contraception (refer to [Section 4.3.2](#) for female subjects and [Section 4.3.3](#) for male subjects). The discussion must be documented in the subject's source documents.
11. PGA of Disease Activity.
12. Patient/Parent Global Assessment, according to the subject's age at the time of the assessment.
13. Pain Assessment. The Pain Assessment should be completed before the Joint Assessment.
14. Duration of Morning Stiffness.
15. Joint Assessment.
16. Overall Back Pain and Nocturnal Back Pain (ERA subjects only).
17. BASMI Assessments (ERA subjects only).
18. BSA (PsA subjects only).
19. PGA of Psoriasis (PsA subjects only).
20. CHAQ or HAQ, according to the subject's age at the time of the assessment.
21. Adverse events, including malignancies, serious adverse events, infections, medically important infections, and injection site reactions.
22. Review inclusion/exclusion criteria and discuss the option of entering into the observational period or the re-treatment period as appropriate.

- For subjects experiencing disease relapse who are being considered for participation in the re-treatment period, review inclusion/exclusion criteria that apply to the re-treatment period.
- Those subjects who do not meet entry criteria for the re-treatment period will be asked to participate in the observational period.
- For subjects entering into the observational period, sign and date informed consent/assent for the observational period.

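### Protocol 6.1.2.2 and 6.1.2.3 repeat the eligibility check at every visit, the Schedule of Activities does not, and in the withdrawal period the repeated check cannot be passed as written

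*Protocol*

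**What the plan says.** **Withdrawal period, text.** The list in Protocol 6.1.2.2 opens: "The following assessments will be performed at all visits during the withdrawal period unless otherwise indicated". Item 1 is the check of the withdrawal-period criteria. Item 2 gives the consequence: "Those subjects who do not meet entry criteria for the withdrawal period will be asked to participate in the observational period". The same section says that subjects without relapse stay in the withdrawal period until 96 months after study baseline.

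**Withdrawal period, criteria.** Exclusion 3 of Protocol 4.2.3 reads: "Prior and/or current participation in the withdrawal/re-treatment period of study B1801023".

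**Re-treatment period, text.** Protocol 6.1.2.3 opens its list with "The following assessments will be performed at all visits during the re-treatment period". Item 1 is the check of the re-treatment criteria, and item 2 reads: "Those subjects who do not meet entry criteria for the re-treatment period will be asked to participate in the observational period". The introduction says that subjects continue for as long as they stay eligible for re-treatment.

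**Tables.** The withdrawal table reviews the withdrawal criteria at Day 1 only. For subjects coming from active treatment, the active-treatment table puts that review at the early withdrawal visit. The re-treatment criteria are reviewed at the re-treatment assessment visit and once more in the re-treatment table, where footnote i says: "Applies to the Month 3 visit".

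**Laboratory exclusions.** For blood drawn at the start of re-treatment, 4.2.3.1 item 6 says "the subject may be withdrawn from investigational product at that time". For the re-treatment assessment visit sample, 6.1.5 says "tests should be repeated and decisions regarding continuation of investigational product must be discussed" with the sponsor's clinical team.

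**The concern.** A site can find two rules for the same visit. Under the text, eligibility is reopened at each visit and a subject who fails is invited into observation. Under the tables, it is settled at entry, with one later confirmation at Month 3 of re-treatment.

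The choice has lasting consequences. A subject in observation cannot go back to investigational product (Protocol section 3), and collection shrinks to serious adverse events, malignancies, medically important infections and selected medications (6.1.6). SAP 3.2 and 3.3 restrict the withdrawal and re-treatment analysis sets to data collected in those periods, so a move to observation ends that subject's contribution. In re-treatment the loss could also be selective: if laboratory exclusions are re-applied, follow-up is cut short in subjects with abnormal results, whose on-drug course bears on the secondary objective of long-term safety.

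**Working it through.** The plan states no figure for this point. The check is a visit count and a comparison of sections.

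**Step 1. Scheduled visits after entry (table columns).**

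- Withdrawal: Months 1, 3, 6, 9 (4) + Months 12 to 84 yearly (7) + Months 18 to 90 yearly (7) + Month 96 (1) = 19.
- Re-treatment: Months 3, 6, 9 (3) + four yearly series of 7 visits starting at Months 12, 15, 18 and 21 (28) + Month 96 (1) = 32.

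Both are ceilings. Follow-up ends 96 months after study baseline, so a subject who enters either period later has fewer visits.

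**Step 2. Eligibility checks at those visits.**

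| Period | Text | Tables |
|---|---|---|
| Withdrawal | 19 of 19 | 0 of 19 |
| Re-treatment | 32 of 32 | 1 of 32 (Month 3) |

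The qualifier at the head of the 6.1.2.2 list does not close the gap. Items 6, 8, 9 and 25 to 27 carry their own visit limits; items 1 and 2 carry none. The 6.1.2.3 list has no such qualifier.

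**Step 3. Can the withdrawal check be passed?** Anyone attending a visit in the withdrawal period is a current participant in the withdrawal/re-treatment period. Exclusion 3 of 4.2.3 is therefore true of every such subject at every visit after entry. Applied literally, all fail at Month 1. This contradicts both 6.1.2.2 and footnote c of the withdrawal table, which keep subjects without relapse to Month 96.

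**Step 4. Laboratory exclusions in re-treatment.** Section 6.1.2.3 schedules laboratory tests at Months 3, 6, 9, 12 and every 6 months thereafter: 3 visits (Months 3, 6, 9) + 15 visits (Months 12 to 96 in steps of 6, since (96 − 12)/6 + 1 = 15) = 18 at most. Item 6 of 4.2.3.1 is judged on the latest available results. The relevant sections then say:

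- 4.2.3.1 item 6: the instruction on an exclusionary result covers the sample drawn at the start of re-treatment.
- 6.1.5: repeat and discuss, for the assessment-visit sample only.
- 6.1.2.3 items 1 and 2: a check at all visits, with referral to observation on failure.
- Re-treatment table: no check after Month 3, so none at the 17 later laboratory visits.
- 6.3: the mandatory withdrawal list names none of these laboratory thresholds. Its entry for confirmed blood dyscrasia may overlap some haematology exclusions.

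For a sample after the start of re-treatment, only 6.1.2.3 would turn a value in the exclusion range into a referral. The table and 6.3 give no sign that this is meant.

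**The case against.** The strongest reply is that nobody would read the withdrawal section literally. Section 4.2.3 is headed for subjects planning to enter, item 2 of 6.1.2.2 speaks of entry criteria, and exclusion 3 plainly implements the rule that the period may be entered only once. Section 6.1.4 does class current participants as failing the entry criteria, but in a list shared with the re-treatment early withdrawal visit, where it naturally describes subjects leaving re-treatment. This stands as evidence of intent: a one-time check is the likely meaning. It does not remove the contradiction in the text.

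Four stronger inferences are tempting, and the documents do not support them:

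- *The withdrawal analysis set would be emptied.* SAP 3.2 keeps everyone who entered the period. What could be lost is later follow-up. Subjects are also asked to join observation, under a separate consent, not transferred automatically.
- *A raised ALT at any point in re-treatment triggers three conflicting instructions.* The instructions in 4.2.3.1 and 6.1.5 concern the sample at the start of re-treatment and can be read together. They do not govern later samples. Those fall under 6.1.2.3 and the general rule in 7.2 to repeat and follow clinically significant abnormal values.
- *The Month 3 check is a mistake.* Section 6.1.5 lets dosing begin before the laboratory results are available and requires their review before the first re-treatment visit. Month 3 is that visit, so a confirmation there has a plausible purpose.
- *Re-treatment eligibility was meant to be entry-only.* The statement in 6.1.2.3 that subjects continue while they remain eligible points towards a continuing check, and several 4.2.3.1 exclusions overlap with rules that apply throughout treatment.

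**Conclusion.** The inconsistency holds and is wrong as written. Text and tables differ at all 19 scheduled visits after entry to the withdrawal period and at up to 31 of 32 re-treatment visits (32 − 1). In the withdrawal period the literal check has no possible pass. In re-treatment the open question is whether the 4.2.3.1 criteria, above all the laboratory exclusions, apply after entry.

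The effect is on how much withdrawal-period and re-treatment-period data is collected, and on whether that depends on the page a site follows. A reader might infer harm to the primary objective, but none is shown: malignancy, serious adverse events and medically important infections are still collected in observation, and SAP 5.5 summarises them over all periods. The number of subjects affected cannot be derived from the documents, because it depends on how sites read the text and on how many subjects agree to move to observation.

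The conclusion assumes that the table rows are reproduced correctly and that items without a visit limit mean what the list openings say.

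**What to change.** Reconcile text and tables by a clarifying amendment.

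- **Withdrawal period.** State in 6.1.2.2 that items 1 and 2 apply at the visit of entry (Day 1, or the active-treatment early withdrawal visit), or exempt exclusion 3 of 4.2.3 from any later check.
- **Re-treatment period.** The sponsor should state which 4.2.3.1 criteria, if any, are re-applied after entry, and at which visits. Then 6.1.2.3, the re-treatment table (including the Month 3 check), 4.2.3.1 item 6, 6.1.5 and 6.3 should be made to agree, including on what follows when a later laboratory value lies in the exclusion range.

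Whether eligibility in re-treatment is entry-only or continuing, and how abnormal values are handled, is a clinical choice for the sponsor; this point proposes neither. The clarification itself costs wording in a few sections and, if needed, one table row. Extra visits, procedures or subjects are not required.
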